**Critical and Overall errors**

- Subject pressed the green piercing button **once** and released the button (Note: if subject pressed the piercing button more than once, check 'No')
- Subject **did not** shake the inhaler after piercing the capsule (Note: A 'Yes' response means the subject did not shake the inhaler)
- Subject **does not** breathe out (exhale) into the mouthpiece. (Note: a "Yes" response indicates that the subject did not breathe into the mouthpiece.)
- Subject closed his/her lips tightly around the mouthpiece
- Subject heard or felt the capsule vibrate (rattle) Note: The HCP may need to ask the subject if they heard or felt the capsule vibrate (rattle)

**For CMH sensitivity analysis:**

An ordinal variable (error) will be derived to indicate where a participant had any error, or any critical error whilst demonstrating correct device use. If the subject has an overall/critical error the error=Y whilst if they did not have an overall/critical error then error=N. The variables errty/errtycd will be used to determine whether the variable error is referring to a critical or overall error.

An ordinal variable (err\_ord) will be derived to indicate the responses of critical error based on comparing responses for the device sequences used. This variable will be used in the sensitivity analysis for critical error data.

If the sequence of inhaler use is ELLIPTA inhaler in the 1st period and DISKUS + HandiHaler inhalers in the 2nd period, then for critical error in relation to sequence:

- error\_ord = -1, if subject had critical error in the 1st period but NOT in the 2nd period
- error\_ord = 1, if subject had critical error in the 2nd period but NOT in the 1st period
- error\_ord = 0, if subject had critical errors in BOTH periods or had NO critical errors in BOTH periods

If the sequence of inhaler use is DISKUS + HandiHaler inhalers in the 1st period and ELLIPTA inhaler in the 2nd period, then for each preference question:

- error\_ord = -1, if subject had critical error in the 1st period but NOT in the 2nd period
- error\_ord = 1, if subject had critical error in the 2nd period but NOT in the 1st period
- error\_ord = 0, if subject had critical errors in BOTH periods or had NO critical errors in BOTH periods

The above method also applies to overall errors.

Note: Only error\_ord = -1 or 1 will be used within the analysis. The coding of error\_ord = 0 is only to ensure that this data can be excluded.

**10.6.2.2. Responses to Preference Questions****Preference Questions**

An ordinal variable (pref\_ord) will be derived to indicate the responses to preference based on the sequence of inhaler use. This variable will be used in the statistical analysis for preference data.

If the sequence of inhaler use is ELLIPTA in the 1st period and DISKUS + HandiHaler in the 2nd period, then for each preference question:

- pref\_ord = -1, if subject prefer ELLIPTA
- pref\_ord = 1, if subject prefer DISKUS + HandiHaler
- pref\_ord = 0, if subject has no preference

If the sequence of inhaler use is DISKUS + HandiHaler in 1st period and ELLIPTA in 2nd period, then for each preference question:

- pref\_ord = 1, if subject prefer ELLIPTA
- pref\_ord = -1, if subject prefer DISKUS + HandiHaler
- pref\_ord = 0, if subject has no preference

**10.6.2.3. Number of maintenance COPD****Number of maintenance COPD inhalers**

The covariate of number of maintenance COPD inhalers will be calculated using the CONMED page in the eCRF.

To calculate this all inhaled medications will be counted if:

- They were delivered by a device for  $\geq 4$  weeks prior to randomisation (as per inclusion criteria in the protocol)
- The subject was still using the device at the time of randomisation
- The reason for medication is 'COPD'
- The frequency is not 'PRN' as this is used to denote rescue medications

These devices will then be summed in order to find the total number of COPD maintenance inhalers per subject..

## 10.7. Appendix 7: Reporting Standards for Missing Data

### 10.7.1. Premature Withdrawals

Element	Reporting Detail
General	
 
• For reporting purposes, subject study completion will be defined as completion of all two randomised periods (both devices and questionnaire) on the day of study visit.
 
• Withdrawn subjects will be defined as those who used at least one device once but did not complete all assessments.
 
• Withdrawn subjects will not be replaced in the study.
 
• All available data from subjects who were withdrawn from the study will be listed and all available planned data will be included in summary tables and figures, unless otherwise specified.
 

### 10.7.2. Handling of Missing Data

Element	Reporting Detail
General	
 
• Missing data occurs when any requested data is not provided, leading to blank fields on the collection instrument : 
 
○ These data will be indicated by the use of a “blank” in subject listing displays. Unless all data for a specific visit are missing in which case the data is excluded from the table.
 
○ Answers such as “Not applicable” and “Not evaluable” are not considered to be missing data and should be displayed as such.
 
○ As subjects need to be assessed for errors on both devices, if they only complete one period (one device) they have their missing data imputed as described in Section 10.7.2.2. Subjects who complete both devices, but do not answer the preference questionnaire will be included in the primary analysis as completed without any imputations.
 
 
 

Outliers	
 
• Whilst outliers are not anticipated within this study any subjects excluded from the summaries and/or statistical analyses will be documented along with the reason for exclusion in the clinical study report.
 

#### 10.7.2.1. Handling of Missing and Partial Dates

Element	Reporting Detail
General	
 
• Partial dates will be displayed as captured in subject listing displays.
 

Concomitant Medications/ Medical History	
 
• Partial dates for any concomitant medications recorded in the CRF will be imputed using the following convention: 
 
○ If the partial date is a start date, a '01' will be used for the day and 'Jan' will be used for the month
 
○ If the partial date is a stop date, a '28/29/30/31' will be used for the day (dependent on the month and year) and 'Dec' will be used for the month.
 
 
 
• The recorded partial date will be displayed in listings.
 

**10.7.2.2. Handling of Missing Data for Statistical Analysis**

Element	Reporting Detail
Correct Use and Questionnaire	

• If part or all of a correct use assessment is missing then the whole assessment will be considered missing. For example if a subject has data for DISKUS but not HandiHaler then this will be considered missing data for the 'DISKUS + HandiHaler' assessment. The only exception will be when they had an error on the device that they did complete in which case the assessment will be set to an error.

• All missing data will be handled according to estimand of interest as described within the main body of the RAP

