Assessment of errors will be conducted by health care professionals trained in the correct inhaler use of the three inhalers prior to the start of the study based on the checklist of errors. After randomization, participants will be asked to read the PIL of the first inhaler (s) and then asked to demonstrate correct inhaler use, if they do not demonstrate correct use they will be instructed verbally on correct use by the HCP. A baseline assessment will be conducted when the participant is initially dispensed the inhaler (s) and a second assessment will be conducted after each 28 day dosing period. After demonstrating correct use at Visit 1, the participant will be sent home with the inhaler and the PIL for the first 28 day treatment period. At Visit 2, two checklists shall be completed, the first checklist will be for the Day 28 assessment of the first inhaler (s) and the second checklist will be another baseline assessment for the second inhaler (s) dispensed.

A health care professional trained on the inhalers will assess the participant's ability to correctly use the returned inhalers. Either the ELLIPTA checklist or the DISKUS + HandiHaler combination checklist will be utilized after 28 days of treatment depending on the inhaler (s) returned. Individual checklist assessment of the DISKUS and the HandiHaler will not be assessed. Compliance with returned inhalers (based on the dose counter for the ELLIPTA and DISKUS and remaining capsules for the HandiHaler) will also be assessed by study staff at Visits 2 and 3. A Preference Questionnaire will also be administered and reviewed by study staff at Visit 3 or the last clinic visit.

Overall Design:

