#### 7.1.4. Strategy for Intercurrent (Post-Randomization) Events

There are three intercurrent events identified which could impact upon the estimand of interest:

- The subject could withdraw from randomised study device sequence and therefore withdraw from the study
- The subject could change their standard COPD maintenance medication device to one delivered via ELLIPTA, DISKUS or HANDIHALER; these subjects should have been withdrawn from the study according to the protocol.
- The subject could attend the visit without the device/s they were randomised to, in which case correct use cannot be assessed as described in the protocol.

Rescue Medication use and change to maintenance COPD medication which is not delivered via ELLIPTA, DISKUS or HANDIHALER are not considered intercurrent events.

Subjects who withdrew in period 2 complete an error assessment at the early withdrawal visit, however no error assessments were made if they withdrew in period 1

Two estimands will be assessed:

- **Primary Estimand:** The treatment effect to be estimated is the principle strata of all subjects who stayed on their randomised study device sequence and did not change their standard COPD maintenance medication device to one delivered via ELLIPTA, DISKUS or HANDIHALER, throughout both 28 day treatment periods. In this analysis subjects with intercurrent events will have their data set to missing from the point of that event and so are not included in this analysis. Data from the early withdrawal visit will not be used.
- **Supplementary Estimand:** The treatment effect to be estimated will be the composite effect of initial randomized treatment. Error assessment from the early

withdrawal visit will be used for those who withdrew prematurely from the study in period 2. For those who withdrew without providing an assessment in period 2 it will be assumed that they made an error.

If subjects experience an intercurrent event in Period 1 then they should not have entered Period 2 and so their data in Period 2 will be set to missing for all estimands.

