### 10.6.2. Efficacy

#### 10.6.2.1. Critical and Overall Errors

Critical and Overall errors

If a subject answered 'No' to any of the following it is considered a critical error for the ELLIPTA device:
 
 
Subject slides the cover completely down to expose the mouthpiece until a "click" is heard.
 
Subject does not shake the inhaler after the click is heard upon opening cover. (Note: a "Yes" response indicates that the subject did not shake the inhaler after the click is heard.)
 
Subject does not breathe out (exhale) into the mouthpiece. (Note: a "Yes" response indicates that the subject did not breathe into the mouthpiece.)
 
Subject places mouthpiece between lips, and closes lips firmly around it.
 
Subject takes one long steady deep breath in through their mouth.
 
 
If a subject answered 'No' to any of the following it is considered a critical error for the DISKUS device:
 
 
Subject opened cover
 
Subject slid the lever away from the mouthpiece as far as it would go until it clicked. Note: If the subject presses the lever more than once or slides the lever back to its starting position, this box should be checked No.
 
Subject did not tilt or shake the device after dose preparation Note: A Yes response means the subject did not tilt or shake the inhaler after preparing the dose
 
Subject did not exhale into the mouthpiece
 
Subject placed the mouthpiece between his/her lips
 
 
If a subject answered 'No' to any of the following it is considered a critical error for the HandiHaler device:
 
 
Subject opened the mouthpiece by pulling the mouthpiece ridge up and away from the base so the center chamber is showing
 
Subject appropriately only opened 1 capsule from the blister card
 
Subject placed the capsule in the center chamber of the inhaler
 
Subject closed the mouthpiece against the gray base, a click was heard, and the dust cap was left open
 

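### The missing-item rule in SAP 10.7.2.2 discards errors already recorded on partly blank checklists, and its exception can protect the two-device comparator but never ELLIPTA

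*SAP*

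**What the plan says.** SAP 10.7.2.2 gives the base rule: "If part or all of a correct use assessment is missing then the whole assessment will be considered missing". It illustrates the rule with the two-device regimen: "For example if a subject has data for DISKUS but not HandiHaler then this will be considered missing data for the 'DISKUS + HandiHaler' assessment". It then allows one exception: "The only exception will be when they had an error on the device that they did complete", in which case the assessment counts as an error.

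Protocol 5.1 fixes the unit of assessment: "Either the ELLIPTA checklist or the DISKUS + HandiHaler combination checklist will be utilized after 28 days of treatment depending on the inhaler (s) returned". ELLIPTA therefore has one checklist for one device. The comparator has one combined checklist covering two devices, and SAP 10.6.2.1 lists its critical items device by device.

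For everything else that is missing, 10.7.2.2 sends the reader to the estimands in 7.1.4. There the supplementary estimand assigns an error only to a defined group: "For those who withdrew without providing an assessment in period 2 it will be assumed that they made an error".

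**The concern.** The primary endpoint (SAP 7.1.1) is having zero errors. One item scored No settles it, whatever the other items would have shown. A rule that sets such an assessment to missing throws away a known outcome.

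The exception shows that the authors accept this logic, but its condition is a completed device. A DISKUS error is kept when HandiHaler is blank, because DISKUS was completed. A partly blank ELLIPTA checklist has no other device that could have been completed, so an error recorded on it is lost. An error on a partly blank DISKUS or HandiHaler checklist is also lost, unless the other device was completed with an error.

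The primary model (SAP 7.1.5.1) is conditional logistic regression stratified by participant, so anyone with one period missing contributes nothing. At stake is a small shift in the primary odds ratio, decided by a data-handling sentence in an open-label comparison. The zero-critical-error endpoint uses the same model and inherits the rule.

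**Working it through.** **The plan's own figure.** Protocol 10.2 claims at least 90% power with 216 evaluable participants for each Table 1 pair. Simulation with 108 per device sequence, independent outcomes and a two-sided 5% test gives 95.1%, 95.3%, 93.8%, 95.7% and 93.9%. Enrolment is 216/0.9 = 240. Both figures reproduce, and this point does not affect them.

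**Does another rule recover these cases?**
- SAP 7.1.4 names three intercurrent events: withdrawal, switching to one of the study devices, and attending without the device. A blank item is none of these.
- The assumed-error rule needs a withdrawal with no Period 2 assessment. A completer with a partly blank checklist does not qualify.
- The tipping point in 7.1.5.1 varies missing Period 2 assessments, for the supplementary estimand only. Period 1 checklists are untouched.
- SAP 10.7.2 points to 10.7.2.2 for imputation, and 10.7.2.2 points back to the estimands.

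**Size when blanks fall on checklists with an error.** The share s of erring device checklists that also have a blank is not in the documents. I assume 2%, 5% and 10%, the same for all three devices. Let p be the true error rate on both regimens (null case). The odds ratio (OR) is for zero errors, so values above 1 favour ELLIPTA.

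- ELLIPTA errors kept: p(1 − s).
- Comparator, errors coinciding on both devices: lost only if both checklists are partly blank, so p(1 − s²) are kept. OR = (1 − s²)/(1 − s) = 1 + s = **1.02 / 1.05 / 1.10**. Simulated averages run slightly higher, to about 1.11 at the top, with type I error about 5% to 8%.
- Comparator, independent errors: the per-device rate is d = 1 − √(1 − p). Kept: 2d(1 − d)(1 − s) + d²(1 − s²). OR = 1 + s·d²/p. With p = 0.35, d = 0.194 and d²/p = 0.107, so OR = **1.00 / 1.01 / 1.01**.

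The coinciding case is the one Protocol 10.2 adopts when it assumes that participants error-free on one comparator device are error-free on the other.

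**In participants.** With 20% vs 35% error rates, 216 participants and independent outcomes, there are 216 × 0.20 = 43.2 ELLIPTA errors. The rule loses 0.9 / 2.2 / 4.3 of them. Of these, 0.6 / 1.4 / 2.8 come from the 216 × 0.20 × 0.65 = 28.1 informative ELLIPTA-only pairs.

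**If blanks are unrelated to errors.** Let each device checklist be incomplete with probability g = 2% / 5% / 10%.
- Dropping ELLIPTA checklists at random does not by itself move the OR, because (1 − g) cancels.
- The comparator still behaves unevenly. With coinciding errors the current rule gives (1 − g²)/(1 − g)² = (1 + g)/(1 − g) = 1.04 / 1.11 / 1.22. With independent errors it gives 1.02 / 1.06 / 1.12. Type I error at a true 35% on both regimens is 5.3% / 7.5% / 14.4% and 5.1% / 5.5% / 7.7%.
- The factor (1 + g) comes from the uneven exception. The factor 1/(1 − g) arises because an error-free comparator result needs two complete checklists. Rewording the rule removes only the first factor.

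**The case against.** The strongest reply is that the intent is readable. The exception and the only example are at device level, and both suggest that a known error should count. Items are Yes/No boxes completed by a trained professional, and data are monitored and cleaned, so blanks may be rare. All of that stands, and it is why the size is small. It does not change what a programmer would code from the sentence as written.

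A second reply is that the comparator has two devices and more items, so it may lose as many errors as ELLIPTA or more. This partly stands. At 33% vs 50% with s = 10% and independent device errors, ELLIPTA loses 3.3% of assessments. The comparator (d = 1 − √0.5 = 0.293) loses 0.414 × 0.10 + 0.086 × 0.01 = 4.2%. What moves the odds ratio, however, is the share of errors lost: 10% on ELLIPTA and 4.2/50 = 8.5% on the comparator. The direction toward ELLIPTA does rest on equal blank rates. With independent errors at p = 0.35, the comparator loses about 2 × 0.194 × 0.806/0.35 = 0.89 of the ELLIPTA share, so a comparator blank rate about 1/0.89 = 1.12 times as high would cancel the shift.

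A reader might infer that later steps go blank because the demonstration stopped after an early failure, so that losses concentrate on failures. No section says so. The mock listing EFF_L01 in SAP Appendix 11 shows an ELLIPTA checklist with both a failure to open the cover and a later exhalation error, which suggests scoring continues.

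**Conclusion.** The point holds as a defect in wording with a small, directional consequence. Read literally, 10.7.2.2 discards known failures, always for a partly blank ELLIPTA checklist and only sometimes for the comparator. Nothing recovers the Period 1 cases. If 2% to 10% of erring checklists have a blank, at the same rate on all devices, the null odds ratio is about 1.00 to 1.01 with independent DISKUS and HandiHaler errors. It is about 1.02 to 1.11, with type I error about 5% to 8%, if those errors coincide. The blank rate is an assumption throughout. At the low end about one participant is affected.

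Two stronger readings are not supported:
- A reader might infer that type I error could reach 9% to 19%. That would need 5% of all ELLIPTA checklists to be lost with a recorded error, which is 5/33 = 15% or 5/20 = 25% of the failing ones, with no loss on the comparator. No figure in the documents supports this.
- A reader might also infer from SAP 10.7.2, where answers such as not evaluable "are not considered to be missing data and should be displayed as such", that an unjudged step is scored as correct. That sentence is a general display convention. The checklist page is not in the documents, and SAP 10.6.2.1 describes Yes/No items.

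**What to change.** Reword SAP 10.7.2.2 along these lines, identically for ELLIPTA, DISKUS and HandiHaler: *If any item on any device checklist is recorded No, the assessment is an error (a critical error if that item is critical), whether or not other items are blank. If no item is No and one or more is blank, the assessment is missing.*

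Report the number of incomplete checklists by regimen, split by whether an error was recorded. Rerun Table 2.06 counting incomplete checklists without an error first as correct and then as errors.

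The cost is two sentences, one count and one bounding rerun, with no new data. If blanks follow errors, the reworded rule returns the null odds ratio to about 1.00.

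The downside is that incomplete checklists are kept only when they contain an error, so error rates are overstated if blanks are random. With random blanks on all three devices the null odds ratio is then 1/(1 − g) = 1.02 / 1.05 / 1.11 at 2% / 5% / 10% (up to about 1.12 in simulation), which is no worse than the current rule. If random blanks fall on ELLIPTA alone, the shift goes the other way: at 20% vs 35%, from 2.15 to 2.11 / 2.05 / 1.94. The bounding rerun makes either effect visible.

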**7.1.5.1. Statistical Methodology Specification**

Endpoint

 
Percentage of participants with zero errors after 28 days of use
 

Model Specification

 
The primary endpoint of the percentage of participants with zero errors after 28 days of use, will be analysed using the Intent-to-treat population.
 
This endpoint will be analysed using conditional logistic regression with subject as fixed strata, and treatment option and period as fixed effects.
 
If there are low cell counts (<5) in the cross tabulation of subjects making errors on ELLITPA compared to DISKUS + HandiHaler or the model fails to converge with all cell counts >=5, then the exact conditional logistic regression with subject as fixed strata, and treatment option and period as fixed effects will be used instead.
 

Model Checking & Diagnostics

 
None
 

Model Results Presentation

 
The odds ratio, 95% CI and p-value will be presented for the comparison between treatment options. It will be based on a two-sided hypothesis testing approach of superiority.
 

Sensitivity and Supportive Analyses

 
A sensitivity analysis will be performed using the Cochran-Mantel-Haenszel (CMH) test. The CMH test serves as a stratified approximation to the Mainland-Gart test, a variation of a one-sample chi-square test that accounts for study inhaler sequence (period). A subject who had an error with both devices or who had no errors with both devices does not provide any information about the superiority of either device. Only those subjects who had error(s) in one device and had no error in the other device are counted for in the Mainland-Gart test.
 
For the supplementary estimand a tipping point analysis will be performed to assess how robust the composite estimand is to missing data assumptions. To assess this the outcomes for subjects with missing error assessment in period 2 will be varied in the two treatment groups independently from imputing 0 subjects with an error to all subjects with an error.
 

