**10.10.5. Efficacy Tables**

Overall Summary of Errors					
No.	Population	IDSL / TST ID / Example Shell	Title	Programming Notes	Deliverable
2.01	ITT	EFF_T01	Summary of Errors on ELLIPTA		SAC
2.02	ITT	EFF_T01	Summary of Errors on DISKUS + HandiHaler	Page by DISKUS + HandiHaler Errors, DISKUS Errors and HandiHaler Errors	SAC
2.03	ITT	EFF_T06	Summary of Overall Errors		SAC
2.04	ITT	EFF_T06	Summary of Overall Errors by Age	Use age categories: 40-64, 65-74 and $\geq 75$ .	SAC
2.05	ITT	EFF_T06	Summary of Critical Errors		SAC
Primary Efficacy Tables					
Percentage of Overall Errors					
2.06	ITT	EFF_T04	Analysis of Percentage of Participants making Zero Errors after 28 days use (Primary Estimand: Principle Strata)		SAC
2.07	ITT	EFF_T04	Analysis of Percentage of Participants making Zero Errors after 28 days use (Supplementary Estimand: Composite)		SAC
2.08	ITT	EFF_T09	Tipping Point Analysis of Participants making Zero Errors after 28 days use (Supplementary Estimand: Composite)		SAC
2.09	ITT	EFF_T07	Sensitivity Analysis of Percentage of Participants making Zero Errors after 28 days use (Primary Estimand: Principle Strata)		SAC

Overall Summary of Errors					
No.	Population	IDSL / TST ID / Example Shell	Title	Programming Notes	Deliverable
2.10	ITT	EFF_T07	Sensitivity Analysis of Percentage of Participants making Zero Errors after 28 days use (Supplementary Estimand: Composite)		SAC
Secondary Efficacy Tables					
Percentage of Critical Errors					
2.11	ITT	EFF_T04	Analysis of Percentage of Participants making Zero Critical Errors after 28 days use (Primary Estimand: Principle Strata)		SAC
Number of Overall Errors					
2.12	ITT	EFF_T01	Summary of Number of Errors by Type for each Inhaler after 28 Days of Use	Replace 'Early withdrawal' column with 'Difference (ELLIPTA minus DISKUS + HandiHaler)	SAC
2.13	ITT	EFF_T08	Summary of Number and Change in Errors per Participant for each Treatment Group (V2 and V3) after 28 Days of Use		SAC
2.14	ITT	EFF_T08	Summary of Number and Change in Errors for each Treatment Group in Participants with One or more Errors after 28 Days of Use		SAC
Exploratory Efficacy Tables					
Preference Attributes					
2.15	ITT	EFF_T04	Analysis of Percentage of Participants with Zero Errors after 28 Days of Use, including the Number of Prescribed Maintenance Inhalers as a Covariate.		SAC

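### For a participant who brings only one of DISKUS and HandiHaler and errs on it, SAP 10.7.2.2 says error and 7.1.4 says missing; other one-device assessments count only if they show an error

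*SAP*

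**What the plan says.** SAP 10.7.2.2 makes a correct-use assessment missing when any part of it is missing, and gives DISKUS data without HandiHaler data as its example. It then adds: "The only exception will be when they had an error on the device that they did complete". Such an assessment is scored as an error. Its second bullet reads: "All missing data will be handled according to estimand of interest as described within the main body of the RAP".

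SAP 7.1.4 lists three intercurrent events. The third is: "The subject could attend the visit without the device/s they were randomised to, in which case correct use cannot be assessed" in the way the protocol describes. For the primary estimand, "subjects with intercurrent events will have their data set to missing from the point of that event", and those participants are left out. For an event in Period 1, the section holds that the participant should not have gone on, "so their data in Period 2 will be set to missing for all estimands". The stratum itself is defined as "all subjects who stayed on their randomised study device sequence and did not change their standard COPD maintenance medication device" to one of the three study inhaler types.

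SAP 7.1.5.1 fits a conditional logistic regression with participant as stratum and with treatment and period as effects. It plans a tipping point analysis for the supplementary estimand only, in which "the outcomes for subjects with missing error assessment in period 2 will be varied in the two treatment groups independently". Protocol 5.1 uses one combination checklist for the two comparator devices and no separate device checklists.

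**The concern.** Two issues meet in the primary dataset.

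First, the two sections can give the same participant different outcomes. Someone who brings DISKUS but not HandiHaler and errs on DISKUS is an error under 10.7.2.2 and missing under 7.1.4. Two programmers could build different primary datasets from the same plan.

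Second, when a device is unassessed for some other reason, 10.7.2.2 alone applies, and entry to the analysis depends on the result. A one-device assessment with an error stays in; one without an error drops out. ELLIPTA has no second device, so this can happen only in the comparator arm. The primary model learns only from discordant pairs. With random partials, the added informative pairs are all ones with a comparator error and no ELLIPTA error, which favour ELLIPTA in a superiority test. Added pairs in which ELLIPTA also showed an error are concordant and contribute nothing.

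**Working it through.** **1. The plan's own figures.** Protocol 10.2 gives 216 evaluable, 240 enrolled and at least 90% power. 216 / 0.90 = 240. I simulated 10,000 crossovers per Table 1 pair with the conditional logistic estimate including period. Its log odds ratio is the mean of the two sequence-specific log ratios of discordant counts. Errors on the two options were taken as independent within participant, because no correlation is given. Power was 94.9, 95.4, 93.4, 95.6 and 93.6% for 33/50, 30/47, 20/35, 10/23 and 5/15. The stated figures are reproduced.

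**2. The two sections side by side.**

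| One device assessed | Result on it | SAP 10.7.2.2 | SAP 7.1.4, primary estimand |
|---|---|---|---|
| Other not brought | Error | Error | Missing; Period 2 also missing if in Period 1 |
| Other not brought | No error | Missing | Missing |
| Other incomplete for another reason | Error | Error | Not addressed |
| Other incomplete for another reason | No error | Missing | Not addressed |

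The conflict is the first row, and it requires the third event in 7.1.4 to include one device of two. The deferral in 10.7.2.2 covers missing data, and the exception has already made this case non-missing. The stratum definition does not settle it either: leaving one inhaler at home neither breaks the device sequence nor changes maintenance treatment.

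**3. Size with random partials.** The partial rate *m* is an assumption. Let *p* be the error rate on one comparator device and *Pc* the combined rate, with the ELLIPTA rate equal to *Pc* (no true difference). Two cases:
- independent device errors, p = 0.1, 0.2, 0.3, so Pc = 1 − (1 − p)² = 0.19, 0.36, 0.51;
- fully concordant errors (the protocol 10.2 assumption), p = Pc = 0.15, 0.35, 0.5.

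Complete assessments supply (1 − m)Pc errors. Partials add m × p errors and no zero-error results. Hence null OR = 1 + m × p / ((1 − m) × Pc), where a value above 1 favours ELLIPTA. Independent, p = 0.2, m = 5%: 1 + 0.05 × 0.2 / (0.95 × 0.36) = 1.029. Concordant, m = 5%: 1 / 0.95 = 1.053.

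| m | Participants of 216 | Null OR | False ELLIPTA superiority (nominal 2.5%) | Two-sided error |
|---|---|---|---|---|
| 1% | about 2 | 1.005–1.01 | 2.6–3.0% | 4.8–5.1% |
| 2% | about 4 | 1.01–1.02 | 2.8–3.4% | 4.9–5.2% |
| 5% | about 11 | 1.03–1.05 | 3.4–4.5% | 5.0–5.8% |

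The error rates are from 40,000 replicates per scenario. Setting all partials to missing gives a null OR of 1.00.

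**4. If all partials are not-brought cases treated as intercurrent events.** A Period 1 case loses Period 2 and leaves the conditional model however Period 1 is scored. Only Period 2 cases (sequences A and B, 108 pairs) can matter, and only where ELLIPTA showed no error:

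Informative participants = 108 × m × P(completed device shows an error) × (1 − Pc).

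- m = 2%: from 108 × 0.02 × 0.1 × 0.81 = 0.2 to 108 × 0.02 × 0.5 × 0.5 = 0.5.
- m = 5%: from 108 × 0.05 × 0.1 × 0.81 = 0.4 to 108 × 0.05 × 0.5 × 0.5 = 1.4 (1.35).

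The log OR averages the two sequences, and only one is shifted. The 5% null OR therefore becomes about √1.03 = 1.015 to √1.05 = 1.025.

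**5. Partials that are not random.** Let a device be *k* times as likely to be unassessed if it would show an error. The two rules are equally far from OR 1 at k of about 1.5–1.6 (independent errors) or 2.0 (concordant). Below that, setting all to missing is closer; above it, the 10.7.2.2 rule is. At m = 5% and k = 2–3, the 10.7.2.2 rule gives 0.98–1.01 (independent) or 1.03–1.05 (concordant). All-missing gives 0.95–0.98 or 0.92–0.97.

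**The case against.** The strongest reply is that the plan has one natural reading. The endpoint is zero errors on the combination, so one observed error settles the outcome whatever the second device would show. The not-brought event refers to assessment by the protocol's method, which is one combination checklist, so attending with one device is not a protocol assessment. Setting data to missing acts on data that exist, so it would follow the appendix derivation and override it. The result would be that not-brought cases are missing and other partials follow 10.7.2.2.

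Much of this stands. Scoring an observed error as an error fits the endpoint. The dependence on outcome comes from dropping the error-free partials, not from keeping the others. The proposed reading is sensible, but the plan does not state it, and the deferral sentence reaches only data still classed as missing. The Period 1 point also stands and cuts the size, as step 4 shows.

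Existing displays cover part of the need. Table 2.02 is laid out as "Page by DISKUS + HandiHaler Errors, DISKUS Errors and HandiHaler Errors", Listing 14 shows errors by participant and device, and SAP 10.7.2 documents exclusions with reasons. The tipping point varies missing Period 2 outcomes across both extremes. It does not reach Period 1 or the primary estimand.

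A reader might infer that the primary test is materially biased towards ELLIPTA, or that setting every partial to missing is always the less biased rule. The documents support neither. No partial rate is given, and the single combination checklist suggests a low one. Step 5 shows that the better rule depends on why the device went unassessed.

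**Conclusion.** The conflict is real but narrow. It affects participants who attend with one of the two comparator devices and err on it, on the reading that the 7.1.4 event includes one device of two. For other partials, 10.7.2.2 makes entry depend on the outcome in one arm.

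The severity is minor. The effect is practically nil at 1–2% partials and amounts to a null odds ratio of 1.03–1.05 at 5% if they are random. If all partials are not-brought intercurrent events, it is about 1.015–1.025 at 5%. These sizes rest on assumed partial rates, assumed device error rates and, for the direction towards ELLIPTA, random missingness; with error-dependent missingness the direction is uncertain. What needs correcting is that the primary dataset is not uniquely defined and that no planned analysis bounds the effect for the primary estimand.

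**What to change.** Before database freeze, reconcile SAP 7.1.4 and 10.7.2.2 so that one rule governs one-device assessments in the primary estimand. For example, 10.7.2.2 could say that its error exception does not apply to devices not brought, which 7.1.4 governs. Section 7.1.4 should say whether its event includes one device of two.

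Add one bounding sensitivity run of the primary estimand over both periods. Keep observed errors as errors, and score the no-error partials once as zero errors and once as errors. Each unobserved result is one or the other, so the two runs bracket the full-data result whatever the cause of missingness. With random partials and no true difference they give 0.98–1.00 and 1.04–1.14 at 2%, and 0.96–1.00 and 1.10–1.35 at 5%. A Period 1 not-brought case can enter this run only if its Period 2 assessment is kept, so the plan should say whether it is.

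The cost is a sentence in each section and one extra two-way run, with no change to data collection or sample size. If the sponsor sets all partials to missing, power at 20% versus 35% falls from about 93.7% to 93.2% at 2% and to 92.6–92.8% at 5%, roughly 0.5 to 1 point. If the exception stays for other partials, the lean under random missingness remains and the bounding runs show its size. A count of one-device assessments by device, period, reason and result would help the reader but is optional.
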